16.1 Primary Endpoint Analysis

Analysis Set: ITT/SAF

Tumor assessments will be performed by the investigator primarily according to the RECIST Version 1.1 and secondarily according to the modified RECIST (mRECIST) for HCC (see CTP appendices J and K). The baseline tumor assessment is scheduled to be performed during the screening period. Tumor response evaluations will then be assessed by computed tomography (CT) or magnetic resonance imaging (MRI), whichever was used at the baseline tumor assessment, at the end of every 2 cycles (i.e. before the start of Cycles 3, 5, 7, 9, 11, 13, and every 4 cycles thereafter until PD). Tumor assessments will be performed at the end of treatment visit for subjects whose last tumor assessment was performed \geq 6 weeks prior.

The primary endpoint of this study is PFS status at 12 weeks as assessed by the investigator according to RECIST Version 1.1. Progression-free is defined as a subject having a tumor assessment of Complete Response (CR), Partial Response (PR), Non-CR/non-PD, or Stable Disease (SD) 12 weeks after the start of treatment or later.

The number and percentage of individuals who experienced an event (PD or death) at or before 12 weeks will be presented along with the corresponding two-sided exact Clopper-Pearson (2) 90% CI.

The null hypothesis that the rate of progression-free subjects at 12 weeks is less than or equal to 15% will be tested against a one-sided alternative using a binomial exact test with an alpha value of 0.05.

The primary endpoint analyses will be repeated for the subgroups described in Section 10.

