### 8.1 Sample Size

For Phase Ib, the sample size of up to 18 subjects was not based on any statistical assumptions; rather, it follows the "3+3 rule," a well-established current methodology in the design of dose-finding trials in oncology.

For Phase II, the sample size of 48 subjects was determined as follows. Under the assumption of no treatment effect, the rate of MET+ subjects without progression at 12 weeks (the primary endpoint) was assumed to be ~15% based on historical data. It is expected that MSC2156119J treatment will lead to 30% MET+ subjects without progression at 12 weeks. The null hypothesis (that the true rate of subjects without progression at 12 weeks is  $\leq 15\%$ ) will be tested using a one-stage design based on the exact binomial distribution (5). With a type I error rate of 5% (one-sided) if the true rate of subjects without progression at 12 weeks is  $\leq 15\%$ , to reach a power of 80% if the true rate of subjects without progression at 12 weeks is 30%, this design requires 48 subjects to be treated in Phase II.

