#### 8.3 Endpoints

#### 8.3.1 Primary Endpoints

The primary endpoints for the two parts of the trial are as follows:

- Phase Ib: Incidence of DLTs occurring during Cycle 1. The definition of a DLT for the Phase Ib part of the trial is provided in Section 6.2.2.
- Phase II: Progression-free survival (PFS) status at 12 weeks, defined as 'progression-free' if subject has tumor assessment of CR, partial response, or stable disease (SD) (as assessed by the investigator according to RECIST Version 1.1) 12 weeks after start of treatment or later. In any other case, progression-free status is not regarded as 'progression-free'.

Analyses of these endpoints are described briefly in Section 8.5.2.

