#### 8.3.2 Secondary Endpoints

#### 8.3.2.1 Efficacy Endpoints

Secondary endpoints are as follows:

• TTP, measured as the time (in months) from the date of first study drug administration to the date of radiological confirmation of PD performed according to RECIST Version 1.1. In HCC, TTP is recommended as a sensitive endpoint in measuring antitumor activity of molecularly targeted agents in HCC Phase II trials since it is less vulnerable to the potential confounding effect of underlying liver disease than the traditional endpoint PFS. For this reason, TTP will be regarded as the major sensitivity analysis for the primary endpoint of PFS status.

- PFS, defined as the time (in months) from first study drug administration to either first observation of PD (as assessed by RECIST Version 1.1) or occurrence of death due to any cause within 12 weeks of the last tumor assessment, whichever occurs first.
- PFS, defined as the time (in months) from first study drug administration to either first observation of PD (as assessed by mRECIST for HCC) or occurrence of death due to any cause within 12 weeks of the last tumor assessment, whichever occurs first.
- Time-to-symptomatic progression (TTSP) as subject-reported outcome, defined as the time (in months) from first study drug administration to the date of deterioration of symptoms assessed by FHSI-8 (defined as at least a 4-point increase, i.e., higher score, compared with baseline value), or deterioration to ECOG performance score 4, or death (applicable for Phase II only).
- OS time, defined as the time (in months) from first study drug administration to the date of death.
- Objective tumor response: Subjects with best overall tumor assessment of CR or partial response according to RECIST Version 1.1 from first study drug administration until first occurrence of PD.
- Disease control: Subjects with best overall tumor assessment of CR, partial response, or SD according to RECIST Version 1.1 from first study drug administration until first occurrence of PD. SD must be observed at the end of Cycle 2 or later.
- Biological response as measured by serum AFP, defined as a > 20% decrease in AFP level by Cycle 2 compared with baseline.

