Subjects that developed withdrawal criteria while on the study but were not withdrawn	Other criteria	Subjects that became pregnant during the study and were not withdrawn	PDEV33	Section 5.5.1	Medical review required
Subjects that developed withdrawal criteria while on the study but were not withdrawn	Other criteria	Subjects that had QTc > 500 msec or change of QTc from baseline > 60 msec and were not withdrawn	PDEV34	Section 5.5.1	Programmed to check if QTc > 500 msec or change from baseline > 60 msec
Subjects that developed withdrawal criteria while on the study but were not withdrawn	Other criteria	Subjects that were not compliant with administration of MSC2156119J and were not withdrawn	PDEV35	Section 5.5.1	Medical review required
Subjects that developed withdrawal criteria while on the study but were not withdrawn	Other criteria	Subjects with documented progression of disease that were not withdrawn	PDEV36	Section 5.5.1	Medical review required
Subjects that developed withdrawal criteria while on the study but were not withdrawn	Other criteria	Subjects that initiated other anticancer treatment and were not withdrawn	PDEV37	Section 5.5.1	Medical review required.
Subjects dosing error	Study Medication	Subject had dosing error.	PDEV38	Section 6.2	List if relative dose intensity over or equal to 110% or less than or equal to 90%.
CCI					
Any other protocol deviation which is deemed to be significant but has not been pre-specified in this table	Any	Any	PDEV98	NA	Medical review required
For Clinically Important PD					

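### The Phase II primary endpoint does not require that no PD is dated on or before the qualifying scan at 12 weeks or later, so a subject can be both a primary success and an earlier PFS event

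*SAP*

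**What the plan says.** Success is defined by one later scan. The Phase II SAP, section 16.1, reads: "Progression-free is defined as a subject having a tumor assessment of Complete Response (CR), Partial Response (PR), Non-CR/non-PD, or Stable Disease (SD) 12 weeks". The time runs from first dose, and a later scan also qualifies. Protocol 8.3.1 calls a subject progression-free "if subject has tumor assessment of CR, partial response, or stable disease (SD", by investigator RECIST 1.1) 12 weeks after start or later, and treats all other cases as not progression-free. Protocol 8.5.2 and the synopsis repeat the test.

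Other endpoints carry a limit that this one lacks. Objective response and disease control in Protocol 8.3.2.1 are counted "from first study drug administration until first occurrence of PD", and SAP 16.2.5 runs best overall response up to PD.

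SAP 16.1 also says that subjects with PD or death by week 12 will be counted and shown with a 90% confidence interval. SAP 16.2.1 makes radiological PD a PFS event on the date of PD.

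SAP Appendix 1 has deviation code PDEV36, "Subjects with documented progression of disease that were not withdrawn", and gives it no consequence for the endpoint.

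**The concern.** A subject with a PD dated at week 6 and an SD scan at week 12 meets the success sentence as written. The protocol's default for other cases does not catch this subject, because the success condition is already met. The same subject has a PFS event at week 6 and falls in SAP 16.1's own count of events by week 12. One subject would then sit on both sides of the primary result.

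This matters because the primary endpoint carries the only formal efficacy test, with all treated subjects in the denominator, investigator assessment and no blinding. The gap can only add successes.

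**Working it through.** **Can the case occur?**

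- *Planned stop.* Treatment ends at first radiological PD (Protocol 5.1.2, 5.5.2). On-treatment scans run until PD or drug discontinuation (7.1.3.7). After stopping without PD, scans end at PD or new anticancer therapy (5.5.2). A subject followed this way normally has no scan after PD.
- *Back-dating.* Under Appendix J (New Lesions), an equivocal new lesion is followed on continued therapy. If repeat scans confirm it, PD takes the date of the first scan. The passage on equivocal progression under best overall response works the same way. Take a lesion that is equivocal at week 6, with overall SD at week 12 and confirmation at week 18. PD is dated week 6, and the week-12 SD scan still qualifies. No deviation is needed. If the lesion is first seen as equivocal on the qualifying scan itself, PD is dated on that scan.
- *Off-schedule scans.* Appendix H lets assessments be repeated at unscheduled visits, and SAP section 11 lets such data enter analyses that use post-baseline data.
- *Kept on after PD.* PDEV36 subjects stay in the analysis. All treated subjects are included (SAP 10.2) and there is no per-protocol set (12.2.2).

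**The design figure.** Inputs from Protocol 8.1: the null rate "was assumed to be ~15% based on historical data"; the alternative, "to reach a power of 80% if the true rate of subjects without progression at 12 weeks is 30" percent; and "With a type I error rate of 5% (one-sided"). The sample size is 48. Protocol 8.5.2 rejects the null at 12 or more successes.

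With X ~ Binomial(48, p):
- Type I error = P(X ≥ 12 | p = 0.15) = 0.0478.
- Power = P(X ≥ 12 | p = 0.30) = 0.8186.
- P(X ≥ 11 | p = 0.15) = 0.0956, so 12 is the lowest cut-off that keeps 5%.

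A search over n finds 48 as the smallest size that meets both conditions. The plan's figures reproduce.

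**Effect of one subject at the boundary (exact 90% CI).**

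| Successes | Rate | p | 90% CI |
|---|---|---|---|
| 12/48 | 25.0% | 0.0478 | 15.1% to 37.3% |
| 11/48 | 22.9% | 0.0956 | 13.4% to 35.1% |

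**Effect of an assumed rate.** The documents give none. Let m be the share of true failures counted as successes. Under the null, the counted rate is 0.15 + 0.85m.

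| m (assumed) | Counted null rate | Type I error | Miscounted per trial (48 × 0.85 × m) |
|---|---|---|---|
| 0 | 0.1500 | 0.048 | 0 |
| 1% | 0.1585 | 0.068 | 0.41 |
| 2% | 0.1670 | 0.093 | 0.82 |
| 5% | 0.1925 | 0.200 | 2.04 |

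The 5% row is an outer bound for illustration.

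**The case against.** The strongest reply is that the intent is plain and the schedule does most of the work. The endpoint is named PFS status at 12 weeks, the hypothesis concerns subjects without progression, and SAP 16.1 counts PD or death by week 12. Counting an earlier PD as a success would contradict that section. Target-lesion PD and SD are both judged against the smallest sum on trial (Appendix J), so PD that has not regressed does not become SD. A case would also show in the deviation and PFS listings, the TTP analysis and the independent review in SAP 16.4.1.

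This stands as to frequency and intent. It does not close the gap: the success sentence is what will be programmed, the back-dating route follows the schedule, and a listing does not change the tested count.

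Stronger readings that the documents do not support:

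- *That the type I error is 9.6%.* That is the error of a cut-off of 11. It would apply only if every trial with exactly 11 true successes gained one miscounted subject (0.0956 − 0.0478 = 0.0478 added).
- *That the SAP expects such subjects.* The codes in Appendix 1 turn withdrawal criteria into a checklist. They predict neither deviations nor an SD scan after PD.
- *That an unequivocal week-6 lesion that later resolves is the typical case.* Appendix J asks for unequivocal new lesions and calls progression on non-target disease alone extremely rare.
- *That new anticancer therapy must count as failure.* PDEV37, "Subjects that initiated other anticancer treatment and were not withdrawn", names such subjects, but neither SAP 16.1 nor the PFS rule in 16.2.1 uses new therapy. Adding it to the primary endpoint alone would create a new mismatch with PFS.

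**Conclusion.** The point holds as a gap in the definition, with a small expected effect. Neither the protocol nor the SAP excludes a subject whose PD is dated on or before the qualifying scan, and the plan's own RECIST appendix allows that without a deviation. Such a subject is a primary success and a PFS event at or before the same scan. The subject also enters SAP 16.1's event count if the PD is dated by week 12.

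Two assumptions carry this. PD is dated as Appendix J directs, at the first scan and not at confirmation; and the interim SD assessment stays as recorded, since nothing says that it is re-read. The size is unknown: one subject decides a result at the boundary, and the error rates of 6.8% and 9.3% rest on assumed shares of 1% and 2%. A reader should not infer that failures will enter the numerator routinely.

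**What to change.** In Protocol 8.3.1 and 8.5.2 and Phase II SAP 16.1 (and the synopsis, to match), add to the success definition: *with no RECIST 1.1 PD dated on or before that assessment (including PD back-dated after later confirmation)*. The word *dated* is needed, because back-dated PD is documented after the qualifying scan.

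Also:
- Apply the clause to PDEV36 subjects: a PD dated on or before the scan makes the subject not progression-free.
- In SAP 16.1, tabulate the proportion that is tested, with its 90% interval. The PD-or-death count is not its complement and can be kept as a separate line.
- State one rule for new anticancer therapy, used for both the primary endpoint and PFS.

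The cost is one clause and some programming. The sample size of 48, the cut-off of 12, the type I error of 0.0478 and the power of 0.8186 do not change. The prior-PD clause can only lower the reported rate, and only slightly.

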	• Efficacy parameters (PFS, objective tumor response, disease control, TTP, OS, time to symptomatic progression [TTSP; defined as time from first study drug administration to deterioration of symptoms as assessed by FHSI-8, or by deterioration to ECOG PS 4, or death], and biological response as measured by AFP)
	• Safety parameters (drug exposure; incidence and type of treatment-emergent AEs; incidence and reasons for deaths, including deaths within 33 days after the last dose of MSC2156119J; vital signs; ECG changes; hematology, chemistry, and urinalysis parameters; physical examination including change in body weight; and ECOG PS)
Pharmacokinetics endpoints	Phase Ib:
	• As described in the secondary endpoints
	CCI
Exploratory endpoints	CCI

population, which is defined as all subjects who have been administered at least one dose of study drug.
Phase Ib
The number and proportion of subjects experiencing a DLT will be used as the primary measure to confirm the RP2D. Information regarding safety and PK data beyond Cycle 1 will also be taken into consideration to confirm the RP2D.
The analyses of secondary time-to-event endpoints will follow standard methodology, separately for each dose level.
Rates (response rates, disease control rates) will be summarized along with 2-sided, 90% confidence intervals, separately for each dose level.
Phase II
As a primary analysis, the proportion of subjects who are progression-free at 12 weeks will be estimated, including a 90% confidence interval. The numerator of the estimated rate is the number of subjects in the respective analysis population whose tumor assessment at 12 weeks or later indicates stable disease (SD) or better and the denominator is the number of all subjects in the respective analysis population.
The null hypothesis of no treatment effect of MSC2156119J ( $P \le 0.15$ ) will be tested keeping a one-sided type-I error of 5%. If $\ge 12$ out of 48 subjects are without progression at 12 weeks, the null hypothesis will be rejected and the trial will have met its primary endpoint.
The analyses of secondary time-to-event endpoints will follow standard methodology employing Kaplan-Meier estimates.
Response rates and disease control rates will be summarized along with 2-sided, 90% confidence intervals.

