### 7.1.5 Post-treatment Follow-up Visit

This visit will be performed  $30 \pm 3$  days after the last treatment for subjects who discontinue trial treatment permanently, including subjects who have completed an End of Treatment Visit. If another anticancer therapy will be started before the end of this period (30 days), the Post-treatment Follow-up Visit should be conducted prior to start of this therapy. Subjects who terminated their treatment early, for whatever reason, will be encouraged to return to the clinic for the Post-treatment Follow-up Visit. If the subject is unable to return for the Post-treatment Follow-up Visit, the reason should be clearly documented in the subject's medical record.

The following assessments and examinations will be performed on this day:

- Physical examination including body weight;
- ECOG PS;
- Vital signs;

Document No. CC

- ECG;
- Blood samples (to assess hematology, chemistry, and coagulation);
- Serum pregnancy test (if applicable);
- Urinalysis;
- AE assessment;
- Recording of concomitant medications/procedures;
- FHSI-8 and FACT-HP (Phase II only).

For operational purposes, a Trial Procedure Termination eCRF will be completed for all subjects when no further trial evaluations are expected (with the exception of potential survival follow-up). The following will be recorded in the eCRF: the date of discontinuation from trial procedures, the primary reason for discontinuation from trial procedures, and whether the subject agrees to be followed for survival.

Refer to Figure 4 for a schematic depicting when the Trial Procedure Termination eCRF will be completed. The Trial Procedure Termination eCRF will be completed at the Post-treatment Follow-up Visit for subjects who terminated their treatment due to disease progression, withdrawal of consent, loss to follow-up, or death. Subjects who discontinued trial treatment for all other reasons will continue to have tumor assessments according to the same schedule as subjects who remained on trial treatment. These assessments will continue until disease progression, withdrawal of consent, starting a new anticancer therapy, loss to follow-up, or death, at which time the Trial Procedure Termination eCRF will be completed.

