# 8.5.2 Analysis of Primary Endpoints

For Phase Ib, the primary endpoint will be summarized as the number and proportion of subjects experiencing a DLT occurring during Cycle 1.

Information regarding safety and PK data beyond Cycle 1 will also be taken into consideration to confirm the RP2D.

For Phase II, the primary endpoint is PFS status, evaluated by the proportion of subjects who are progression-free at 12 weeks or later according to RECIST Version 1.1. Subjects are considered to be 'progression-free' if the subject has a tumor assessment of CR, partial response, or SD (according to RECIST Version 1.1) 12 weeks after start of treatment or later. In any other case, the subject is not considered to be 'progression-free'. The proportion of subjects progression-free at 12 weeks will be estimated, including a 90% confidence interval. The numerator of the estimated rate is the number of subjects in the ITT/safety population progression-free at 12 weeks and the denominator is the number of all subjects in the respective analysis population.

The design and hypothesis testing is based on the binomial distribution. The null hypothesis that the rate of progression-free subjects at 12 weeks is  $\leq 15\%$  will be tested against a one-sided alternative.

If 12 or more subjects are considered progression-free at 12 weeks, the null hypothesis will be rejected and the trial will have met its primary endpoint. The test keeps a one-sided type-I error of 5%.

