8.1 Sequence of Analyses

The final analysis will be performed at the end of the trial, 12 months after the last subject's first dose of tepotinib. The final analysis will occur once all trial data is in-house, all data queries are resolved, and the database is fully locked.

9 Changes to the Planned Analyses in the Clinical Trial Protocol

The following are changes to the planned analyses in the clinical trial protocol:

- Physical examination results at baseline will not be presented since these are not collected on the eCRF. Relevant findings had to be entered on the medical history or adverse event eCRF page.
- Relative dose intensity will be summarized rather than treatment compliance.
- The Pd Analysis Set is not defined in this SAP since all Pd related analyses will be carried out on the intent-to-treat (ITT)/safety (SAF) analysis set.
- The deterioration of symptoms assessed by FHSI-8 is defined in accordance with the scoring guidance in appendix 2 as at least a 4-point decrease compared with the baseline value.
- Summaries of sum of longest diameter (SOLD) data are included but these are not explicitly mentioned in the protocol.
- Summaries of quality of life data are included but these are not explicitly mentioned in the protocol.
- Duration of response will be calculated and presented in data listings but this is not explicitly mentioned in the protocol.
- The underlying disease or medical condition related to etiology subgroups will be hepatitis C virus (HCV), and other as opposed to hepatitis B virus (HBV) and other as defined in the protocol.

• 60

• A decrease in AFP level of more than 20% at the Cycle 3 assessment, or the last assessment for subjects that terminated treatment prior to the Cycle 3 assessment, as compared with baseline.

Otherwise, the statistical methods as described in the protocol will be adopted.

10 Protocol Deviations and Analysis Sets

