16.3 Analysis on Subgroups

Subgroups for analysis are defined in Section 10. The analysis of the primary endpoint (number of progression free subjects at week 12) and PFS and OS will be presented by subgroups.

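### Phase II SAP 16.1 puts its exact 90% interval on PD or death by week 12, while the protocol estimates, and the SAP tests, the progression-free proportion; the two are not complements

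*SAP*

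**What the plan says.** **Protocol.** Section 8.5.2 estimates the proportion progression-free at 12 weeks with a 90% confidence interval: "The numerator of the estimated rate is the number of subjects in the ITT/safety population progression-free at 12 weeks", over all subjects in that population. The statistical methods in the synopsis agree; the numerator there is subjects "whose tumor assessment at 12 weeks or later indicates stable disease (SD) or better and the denominator is the number of all subjects". Section 8.3.1 closes the definition: "In any other case, progression-free status is not regarded as" progression-free. A subject without a qualifying scan therefore counts as a failure, whether or not PD or death was recorded.

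**Phase II SAP.** Section 16.1 keeps essentially the same definition: CR, PR, non-CR/non-PD or SD at 12 weeks or later. It tests the progression-free rate against 15% with an exact binomial test at one-sided 0.05. Its display sentence, however, reads: "The number and percentage of individuals who experienced an event (PD or death) at or before 12 weeks will be presented", with the exact 90% interval attached to that quantity. Section 16.1 does not repeat the protocol's rule for all other cases. It also says that the primary analyses are repeated in the Section 10 subgroups.

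No readable bullet in SAP Section 9 lists a change to the primary estimate. That section ends: "Otherwise, the statistical methods as described in the protocol will be adopted".

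**The concern.** The interval planned beside the primary test is for a different quantity from the one tested. If every subject had either an event by week 12 or a non-PD scan at week 12 or later, and none had both, the two intervals would mirror each other. The plan does not guarantee this.

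- **In neither group.** A subject with no PD or death by week 12 and no qualifying scan at week 12 or later. This needs no protocol deviation. Under protocol 7.1.5, scans after treatment stops do not run on regardless: "These assessments will continue until disease progression, withdrawal of consent, starting a new anticancer therapy, loss to follow-up, or death". Read literally, the scan window adds a route. Protocol 7.1.3.7 lets the Cycle 5 scan be taken up to 5 days before the cycle starts and requires it before the start. Cycle 5 Day 1 is day 4 × 21 + 1 = 85. SD on day 80 to 83 followed by PD at the next scan is neither an event by week 12 nor a qualifying scan.
- **In both groups.** Less commonly, a subject with PD before week 12 and a later non-PD scan, as 16.1 is worded. Deviation PDEV36 in SAP Appendix 1 covers "Subjects with documented progression of disease that were not withdrawn", so some progressed subjects may continue.

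In a single-arm trial the estimate and its interval are the main reported result. The risk is a primary table in which the displayed interval and the test appear to disagree.

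**Working it through.** **Inputs.** N = 48, null rate 15%, target rate 30%, one-sided alpha 5%, power 80% (protocol 8.1); reject at 12 or more progression-free subjects (protocol 8.5.2); exact two-sided 90% Clopper-Pearson interval (SAP 16.1). The numbers of subjects in neither or both groups are not in the documents; the values below are illustrations.

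**The plan's own figures.** With X binomial(48, p):

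- P(X ≥ 12 | p = 0.15) = 0.0478 and P(X ≥ 12 | p = 0.30) = 0.8186.
- P(X ≥ 11 | p = 0.15) = 0.0956, so 12 is the smallest valid cut-off.

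The design reproduces.

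**Identity.** Let F be progression-free subjects, E subjects with PD or death by week 12, U subjects in neither group and B subjects in both. Then

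48 = F + E + U − B, so (48 − E)/48 − F/48 = (U − B)/48.

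Each subject in neither group raises 1 minus the event rate above the tested rate by 1/48 = 2.08 points. Each subject in both lowers it by the same amount. In a subgroup of size n the shift is 100/n points per subject.

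**Intervals.** For x of n, the limits are the 0.05 quantile of Beta(x, n − x + 1) and the 0.95 quantile of Beta(x + 1, n − x). For 36 of 48 this gives 75.0% (62.7 to 84.9), which implies 25.0% event-free (15.1 to 37.3). That single displayed line fits several results:

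| Events | Progression-free | Neither | Progression-free rate (90% CI) | One-sided exact p vs 15% | Null rejected |
|---|---|---|---|---|---|
| 36 | 12 | 0 | 25.0% (15.1 to 37.3) | 0.048 | yes |
| 36 | 11 | 1 | 22.9% (13.4 to 35.1) | 0.096 | no |
| 36 | 10 | 2 | 20.8% (11.8 to 32.8) | 0.174 | no |
| 36 | 8 | 4 | 16.7% (8.6 to 28.1) | 0.433 | no |

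In the last three rows the implied event-free interval lies above 15% although the test does not reject.

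**Other direction.** 37 events = 77.1% (64.9 to 86.6), implying 22.9% (13.4 to 35.1). This fits 11 progression-free with none in both groups (p = 0.096, not rejected) and 12 progression-free with one in both (p = 0.048, rejected).

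**The protocol's quantity.** The interval on F/48 agrees with the test on each side of the boundary: the lower limit is 15.1% at 12 of 48 and 13.4% at 11 of 48.

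**The case against.** The strongest reply is that the SAP adds an event display and does not drop the protocol's estimate. SAP Section 11 summarises qualitative variables by counts and percentages of the analysis set, which would cover progression-free status. Section 9 defaults to protocol methods. Section 16.3 describes the subgroup work as "The analysis of the primary endpoint (number of progression free subjects at week 12"), together with PFS and OS. One Section 9 bullet is unreadable, so an unlisted change cannot be proved. SAP 16.2.1 also gives a Kaplan-Meier PFS probability at 3 months with a 90% interval.

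Some of this stands. A percentage progression-free can be read into Section 11, and the absence from Section 9 is only an absence from its readable bullets. The exact test always uses the actual progression-free count, and no document plans to compare the event interval with 15%. The overlap case comes from the endpoint definition, which the protocol shares, and changing the display does not remove it.

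The rest does not. The generic rule in Section 11 provides no interval. Section 9's default and the label in 16.3 do not displace an explicit sentence in 16.1 that specifies the primary display, and no SAP passage states an interval for the progression-free proportion. The Kaplan-Meier figure is a different estimator that censors subjects the protocol counts as failures.

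**Conclusion.** The concern holds. Followed as written, SAP 16.1 reports an exact 90% interval for PD or death by week 12 and not for the proportion that the protocol estimates and the SAP tests. The discrepancy is (neither − both)/48, or 2.1 points per subject, and near the boundary one such subject is enough for the displayed interval and the test to appear to conflict. Subjects in neither group are expected to be the main case, because scans can end without an event; that is a judgement from the follow-up rules. The documents give no frequency, so no overall bias is claimed, and with no such subjects the two intervals mirror each other. The calculations assume 48 treated subjects. The exact test, the 12-of-48 rule, alpha and power are unaffected. This is a reporting error that should be corrected before the final analysis.

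**What to change.** Replace the display sentence in SAP 16.1 with:

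> The number and percentage of ITT/SAF subjects who are progression-free at 12 weeks, with all other subjects counted as not progression-free, will be presented with the two-sided exact Clopper-Pearson 90% CI.

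Use the same quantity in the subgroup repeats. Show the reasons for not being progression-free as descriptive rows: PD by 12 weeks, death by 12 weeks, and not assessable at 12 weeks (no event by then and no qualifying scan at or after it). Define the rows as mutually exclusive within the subjects who are not progression-free, for example by counting death only where no PD came first, so that the table adds up to N.

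The cost is one SAP sentence and the primary table shell with its subgroup versions. No new data are needed and the test does not change.
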